11.2.2. Missing Data

Missing dates and times in the AE data will be handled as described in Section 10.1.1. Concentrations that are marked non-quantifiable in the PK data will be handled as described in the most recent version of the AstraZeneca CPE TFL Standards.

There will be no imputations of other missing data. All subjects will be included in the safety analyses as far as the data permit.

11.2.3. Subject Characteristics

A randomisation listing will be presented and include the following: each subject's randomisation number, the subject's full enrolment number and the treatment to which the subject has been randomised and the country where the study centre is located.

Subjects and/or data excluded from the PK analysis set will be listed including the reason for exclusion. Subject disposition will be summarised and will include the following information: number of subjects randomised and dosed, number and percentage of subjects completing the study and the number and percentage of subjects who were withdrawn (including reasons for withdrawal). Disposition data will be presented based on all subjects randomised.

Subject discontinuations will be listed including the date of study exit, duration of treatment and reason for discontinuation. A listing of informed consent response will also be presented.

11.2.3.1. Demographic and Baseline Data

Demographic variables (age, gender, race, ethnicity, height, weight and BMI) will be listed by subject. Demographic characteristics (age, gender, race and ethnicity) and subject characteristics (height, weight and BMI) will be summarised separately for all randomised subjects. The denominator for percentages will be the number of randomised subjects.

Medical history data will be listed by subject including visit, description of the disease/procedure, MedDRA SOC, MedDRA Preferred Term, start date and stop date (or ongoing if applicable).

11.2.4. Prior and Concomitant Medication and Drug Administration

11.2.4.1. Prior and Concomitant Medication

Prior medications are those that started and stopped prior to the first dose of IMP; all medications taken after first dosing are considered as concomitant (including medications that started prior to dosing and continued after). Prior medication started within 3 months prior to the first dose of IMP will be recorded also in the concomitant medication module of ClinBase™.

Prior and concomitant medication will be listed by subject and will include the following information: reported name, Preferred Term, the route of administration, dose, frequency, start date/time, duration and indication. Prior and concomitant medication will be coded according to the Sponsor's drug dictionary.

The duration will be calculated as:

Duration = end date/time – start date/time + 1

The duration may be presented in hours or days in the listing depending on the applicability to the emerging data. For medications with partial or completely missing start date/times and/or end date/times, the duration will not be calculated.

Medications with missing or partial start date/time and/or end date/time such that it is not possible to classify as prior or concomitant will be considered as concomitant in the listings.

11.2.4.2. Drug Administration

Drug administration dates and times will be listed for each subject and treatment period. Details of high-fat, high-calorie breakfast will be listed.

11.2.5. Safety and Tolerability

All safety data (scheduled and unscheduled) will be presented in the data listings. Continuous variables will be summarised using descriptive statistics (n, mean, SD, minimum, median, maximum) by treatment. Categorical variables will be summarised in frequency tables (frequency and proportion) by treatment. The analysis of the safety variables will be based on the safety analysis set.

Adverse events will be summarised by Preferred Term and SOC using MedDRA vocabulary. Furthermore, listings of SAEs and adverse events that led to withdrawal will be made and the number of subjects who had any AE, SAEs, AEs that led to withdrawal, and AEs with severe intensity will be summarised. Adverse events that occurred from time of informed consent until first administration of IMP will be reported separately.

Tabulations and listings of data for vital signs, clinical laboratory tests and ECGs (listings only) will be presented. Any new or aggravated clinically relevant abnormal medical physical examination finding compared to the baseline assessment will be reported as an AE. Data will be summarised for the observed values at each scheduled assessment, together with the corresponding changes (and/or percentage change) from the baseline when baseline is defined. Clinical laboratory data will be reported in the units provided by the clinical laboratory for the SRC meeting, and in Système International units in the CSR.

Out-of-range values for safety laboratory, vital signs and ECG will be flagged in individual listings as well as summarised descriptively using agreed standard reference ranges and/or extended reference ranges (eg, AZ, program, or laboratory ranges).

11.2.6. Presentation of Pharmacokinetic Parameter Data

A listing of PK blood sample collection times, as well as derived sampling time deviations and all reportable concentrations will be presented for verinurad and for allopurinol and

oxypurinol for all dosed subjects. An additional listing of PK concentrations versus time will be presented for those analytes based on the PK analysis set.

Plasma concentrations will be summarised for the PK analysis set for each time point by treatment for each analyte separately using CSP scheduled times and appropriate descriptive statistics.

All reportable PK parameters from the NCA will be listed for verinurad, allopurinol, and oxypurinol for subjects dosed.

Plasma PK parameters will be summarised for the PK analysis set by treatment for each analyte separately.

Further details on presentation of PK concentration and parameter data will be presented according to the most recent version of the AstraZeneca Corporate CSRHLD reporting standards, that includes applicable descriptive statistics, handling of individual concentrations below the LLOQ for listings, descriptive statistics and figures, and precision and rounding rules for concentrations and PK parameter data.

Individual plasma concentrations versus actual elapsed time after dose will be plotted on both the linear and semi-logarithmic scale with the all dosed treatments overlaid on the same plot and separate plots for each subject and analyte. Plots will be based on all dosed subjects.

Combined individual plasma concentration versus actual times will be plotted based on the PK analysis set on both the linear and semi-logarithmic scale, with all subjects for the same treatment overlaid on the same plot and separate plots for each treatment and analyte.

Geometric mean (+/- geometric standard deviation [gSD]) plasma concentration versus nominal sampling time will be plotted on both the linear scale and semi-logarithmic (no gSD presented) with all treatments overlaid on the same plot and separate plots for each analyte. Plots will be based on the PK analysis set. Focus plots may be provided if there will be no clear distinction among profiles.

11.2.7. Inferential Statistical Analysis of Pharmacokinetic Data

For each individual relative bioavailability comparison, the ratios of C_{max}, AUC_{last} and AUC_{inf} will be calculated for each treatment comparison (Test treatment versus Reference treatment) using log-transformed data.

The following comparisons of relative bioavailability (C_{max}, AUC_{inf} and AUC_{last}) for each analyte (verinurad, allopurinol and oxypurinol) will be performed:

- Treatment 2 versus Treatment 1, ie, “verinurad/allopurinol FDC capsule, fasted” versus “verinurad HPMC capsule and allopurinol tablet, free combination, fasted”.

- Treatment 3 versus Treatment 2, ie “verinurad/allopurinol FDC capsule, fed” versus “Verinurad/allopurinol FDC capsule, fasted”.
- Treatment 4 versus Treatment 1, ie. “verinurad HPMC capsule and allopurinol tablet, free combination, fed” versus “verinurad HPMC capsule and allopurinol tablet, free combination, fasted”.
- Treatment 3 versus Treatment 4, ie. “verinurad/allopurinol FDC capsule, fed” versus “verinurad HPMC capsule and allopurinol tablet, free combination, fed”.
- Treatment 5 versus Treatment 2 (for verinurad only), ie., “verinurad gelatin capsule, fasted” versus “verinurad/allopurinol FDC capsule, fasted”.

The analyses will be performed using a linear mixed-effects analysis of variance model using the natural logarithm of C_{max}, AUC_{inf} and AUC_{last} as the response variables, sequence, period and treatment as mixed-effects, volunteer nested within sequence as a random effect. Transformed back from the logarithmic scale, geometric means together with CIs (2-sided 95%) for C_{max}, AUC_{inf} and AUC_{last} will be estimated and presented. Also, ratios of geometric means together with CIs (2-sided 90%) will be estimated and presented.

11.2.8. Presentation and Statistical Analysis of Pharmacodynamic Data

A listing of sUA sample collection times, as well as derived sampling time deviations will be provided. Serum UA observed and time-matched percentage change from baseline will be listed by treatment and summarized descriptively by treatment and time point. E_{max} CB and tE_{max} CB data will be listed by treatment. For observed and time-matched percentage change from baseline, the descriptive statistics will include n, geometric mean, geometric CV, arithmetic mean, arithmetic SD, median, minimum, and maximum. Geometric CV will be calculated as $100 \times (\text{square root} [\exp(s^2)-1])$ where s is the SD of the log-transformed data.

Individual and mean (with corresponding error bars) serum concentration curves (both linear and log scale) will also be generated. All the results will be based on the PD analysis set.

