- Throughout: The terms 'Test' and 'Reference' were removed to avoid confusion with 'Test product' and 'Reference product'.

The following sections were updated for uniform naming of the different formulations:

- Title Page (Test/Reference Product), Synopsis (Study Rationale, Primary and Secondary Study Objectives, Study Design, Investigational Medicinal Product, Statistical Methods),

Section 1.3 (Rational for Conducting the Study). Section 2 (Study Objectives). Section 3.1 (Overall Study Design and Flow Chart), Section 3.2.1 (Rationale for Study Design), Section 5.1.1 (Procedures for Randomisation), Section 5.4.1 (Table 5-1), Section 11.2.7 (Inferential Statistical Analysis of Pharmacokinetic Data): Updated the current study drug names to the proposed names for the clinical program as per below table.

Previous name in protocol	Proposed full name
12 mg verinurad ph2b capsule	Verinurad prolonged release HPMC capsule 12mg
N/A	Verinurad prolonged release gelatin capsule 12mg
12 mg verinurad + 300 mg allopurinol ph3 fixed-dose combination capsule	Verinurad/allopurinol FDC capsule 12/300 mg
300 mg allopurinol ph2b tablet	Allopurinol tablet 300mg

N/A: not applicable

In addition, the study period has been updated and some minor editorial and formatting changes were made.

PROTOCOL SYNOPSIS

Title of the Study

A Randomised, Single-dose, 5-period, 5-treatment, Crossover Study to Assess the Relative Bioavailability of 4 Different Formulations of Verinurad and Allopurinol in Healthy Subjects.

Principal Investigator (PI)

[name]

Study Centre

This study will be conducted at the Parexel Early Phase Clinical Unit Berlin.

Study Rationale

This study is intended to assess the relative bioavailability between the fixed-dose combination (FDC, ie, verinurad/allopurinol FDC capsule 12/300 mg) and free combination formulations of verinurad (ie, verinurad prolonged release HPMC capsule 12 mg) and allopurinol (ie, allopurinol table 300 mg) in fasted and fed conditions. The study will also assess the relative bioavailability between a formulation only containing verinurad (ie, verinurad prolonged release gelatin capsule 12 mg) and the FDC capsule. For verinurad, all formulations have prolonged release profile. For allopurinol, both formulations containing allopurinol have an immediate release profile.

Number of Subjects Planned

Twenty-five subjects will be randomised into this study to ensure at least 20 evaluable subjects complete the study.

Study Period

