- Treatment 3 versus Treatment 4, ie. “verinurad/allopurinol FDC capsule, fed” versus “verinurad HPMC capsule and allopurinol tablet, free combination, fed”.
- Treatment 5 versus Treatment 2 (for verinurad only), ie., “verinurad gelatin capsule, fasted” versus “verinurad/allopurinol FDC capsule, fasted”.

Presentation and Analysis of Pharmacodynamic Data:

Analyses of sUA will be based on log-transformed values (natural logarithm). Descriptive statistics will be presented for sUA observed and time-matched percentage change from baseline, E_{max} CB and tE_{max} CB by treatment. For observed and time-matched percentage change from baseline, the descriptive statistics will include n, geometric mean, geometric CV, arithmetic mean, arithmetic SD, median, minimum, and maximum. A listing of sUA sample collection times, as well as derived sampling time deviations will be provided.

Sample Size Determination

The sample size was chosen to obtain a reasonable assessment of relative bioavailability between different formulations of verinurad and allopurinol without exposing undue numbers of subjects to the compound at this phase of clinical development. It is estimated that 20 subjects randomised to 5 sequences in a reduced Latin square will provide a 90% CI within 0.7 and 1.43,

with a probability of > 90% if the estimated treatment ratio is 1 for C_{max}. This is based on an intra-subject variability of 24% for C_{max} of verinurad in Study D5495C00001. Similarly, it is estimated that 20 subjects will provide a 90% CI within 0.8 and 1.25, with a probability of > 95% if the estimated treatment ratio is 1 for AUC. This is based on an intra-subject variability of 14.7% for AUC of verinurad in Study D5495C00001.

Twenty-five subjects will be equally randomised to 5 treatment sequences: 12345, 23451, 34512, 45123, and 51234 in order to ensure at least 20 evaluable subjects at the end of the last treatment period.

TABLE OF CONTENTS

PROTOCOL AMENDMENTS	2
Protocol Amendment No. 1, dated 21 January 2021	2
PROTOCOL SYNOPSIS	6
TABLE OF CONTENTS	12
List of Tables	15
List of Figures	15
List of Appendices	16
LIST OF ABBREVIATIONS AND DEFINITION OF TERMS	17
INVESTIGATORS AND STUDY ADMINISTRATIVE STRUCTURE	22
1. INTRODUCTION	25
1.1. Background Information	25
1.1.1. Description of Verinurad	25
1.2. Background to COVID-19	26
1.3. Rationale for Conducting this Study	26
2. STUDY OBJECTIVES	27
2.1. Primary Objective	27
2.2. Secondary Objectives	27
3. STUDY DESIGN	28

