1. INTRODUCTION

1.1. Background Information

Verinurad is a novel URAT1 inhibitor being developed by AstraZeneca to treat patients with CKD and/or HF. By inhibiting URAT1, verinurad prevents UA reabsorption, increases renal UA excretion, and thereby lowers sUA concentrations [1].

The initial development focus for verinurad was for the treatment of gout, which is caused by hyperuricaemia. Therefore, the initial clinical data accumulated on verinurad relate to gout. However, hyperuricaemia is also associated with an increased risk of CKD [2, 3, 4, 5] and HF [6, 7, 8] providing a rationale for developing verinurad in these indications. Despite the established association between hyperuricaemia and CKD and HF, a causal relationship between them remains to be proven.

Potent URAT1 inhibition has been associated with creatinine elevations in a fraction of patients, likely related to increased UA peak concentrations in the proximal tubuli of the kidney. Verinurad is to be developed exclusively in FDC with the XO1, allopurinol, thus also reducing the production of UA and thereby mitigating the risk of creatinine elevations.

The IB describes results from pre-clinical studies, clinical pharmacological studies, and clinical monotherapy and combination therapy with allopurinol [1].

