1.1.1. Description of Verinurad

Verinurad is a potent and specific URAT1 inhibitor. URAT1 is responsible for most of the reabsorption of filtered UA from the renal tubular lumen. By inhibiting URAT1, verinurad increases urine UA excretion and thereby lowers sUA.

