3.3.2. Allopurinol

Allopurinol is a commercially available oral XO inhibitor for conditions where urate/UA deposition has already occurred or is a predictable clinical risk. Allopurinol and its main metabolite oxypurinol inhibit production of and thus lower the level of sUA.

Please refer to the product information sheet of allopurinol tablets [12] for information on PK, PD, and safety.

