10.3. Pharmacodynamic parameters

The PD parameters will be assessed using sUA concentrations, calculating the percentage change from baseline (time-matched, Day -1) in sUA concentrations up to 72 hours post-dose at each timepoint following administration of IMP.

The following PD parameters will be derived from the calculated profiles using non-compartmental analysis with WinNonLin (Version 8.1 or higher):

Serum uric acid derived PD parameters

Emax, CB	Maximum observed percentage change from baseline (Time-Matched, Day -1 and pre-dose on each day) in serum uric acid concentrations
tEmax, CB	Time of maximum percentage change from baseline (Time-Matched, Day -1 and pre-dose on each day) in serum uric acid concentrations

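### Geometric mean and geometric CV are specified for percentage change in serum uric acid, which is expected to be zero or negative for many subjects and times, so these two statistics cannot be computed as written

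*Protocol*

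**What the plan says.** Section 11.2.8 sets out descriptive summaries of sUA by treatment and time point: "For observed and time-matched percentage change from baseline, the descriptive statistics will include n, geometric mean, geometric CV". The sentence goes on to add the arithmetic mean and SD, the median, and the minimum and maximum. One list of eight statistics therefore serves two variables, the observed value and the percentage change. The geometric CV is given by a formula "where s is the SD of the log-transformed data". The synopsis repeats the list and introduces it with "Analyses of sUA will be based on log-transformed values (natural logarithm" as the scale for sUA.

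Section 10.3 defines the variable by "calculating the percentage change from baseline (time-matched, Day -1) in sUA concentrations up to 72 hours post-dose", at each time point after dosing. On the expected direction, Section 1.1.1 says that "verinurad increases urine UA excretion and thereby lowers sUA", and Section 3.3.2 says: "Allopurinol and its main metabolite oxypurinol inhibit production of and thus lower the level of sUA".

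The protocol does not define percentage change through a ratio or log ratio. It gives no sign reversal or offset, and no rule for zero or negative values.

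**The concern.** A geometric mean and a geometric CV exist only when every value is above zero. A percentage change is below zero whenever uric acid has fallen and zero when it has not moved. These are the expected results after a urate-lowering dose, and before the first dose the values should scatter around zero. The rule therefore asks for two statistics that the data are expected not to admit.

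A program that follows the text may return missing values, which is harmless but leaves the specification unmet. It may instead drop the non-positive values and compute on the rest. The geometric mean is then positive by construction, describes only subjects whose uric acid rose, and could sit in the table beside an n that counts everyone. PD is a secondary objective with percentage change as a named outcome measure, so such a figure could be carried into the study report.

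**Working it through.** The plan gives no numerical figure on this point to reproduce. The check is whether the statistics are defined, followed by an illustration of what happens if non-positive values are dropped.

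**Definitions.** For values x:
- geometric mean = exp(mean of ln x)
- geometric CV = 100 × √(exp(s²) − 1), with s the SD of ln x

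Both need ln x for every x. If sUA falls to 0.90 of its time-matched baseline, the percentage change is 100 × (0.90 − 1) = −10, and ln(−10) does not exist. A change of exactly zero fails too. One such value in a cell is enough.

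**Inputs for the illustration.**
- 20 subjects, from the synopsis: "Twenty-five subjects will be randomised into this study to ensure at least 20 evaluable subjects complete the study".
- Size and spread of the sUA effect: not given in the protocol. Assumed here are a geometric mean ratio to baseline of 1.00 down to 0.60 (reductions of 0 to 40%) and an SD of the log ratio of 0.08 or 0.12.
- Ratio log-normal; percentage change = 100 × (ratio − 1); 20,000 replicates per setting.

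**Results.** In every setting essentially all replicates contained at least one non-positive value, so the full-sample statistics were undefined. The last three columns are percentages.

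| True ratio | Log SD | Share positive | Mean no. positive of 20 | P(no subject positive) | Geometric mean of positives only (median over replicates) | Arithmetic mean, all subjects | 100 × (geometric mean ratio − 1) |
|---|---|---|---|---|---|---|---|
| 1.00 | 0.08 | 0.4993 | 9.99 | 0.0000 | +4.48 | 0.3 | 0.0 |
| 1.00 | 0.12 | 0.5007 | 10.01 | 0.0000 | +6.81 | 0.7 | 0.0 |
| 0.95 | 0.08 | 0.2597 | 5.19 | 0.0024 | +3.31 | −4.7 | −5.0 |
| 0.95 | 0.12 | 0.3350 | 6.70 | 0.0002 | +5.50 | −4.3 | −5.0 |
| 0.90 | 0.08 | 0.0943 | 1.89 | 0.1374 | +2.65 | −9.7 | −10.0 |
| 0.90 | 0.12 | 0.1902 | 3.80 | 0.0156 | +4.54 | −9.3 | −10.0 |
| 0.80 | 0.08 | 0.0028 | 0.06 | 0.9456 | +1.71 | −19.7 | −20.0 |
| 0.80 | 0.12 | 0.0310 | 0.62 | 0.5362 | +3.46 | −19.4 | −20.0 |
| 0.70 | 0.08 | 0.0000 | 0.00 | 0.9999 | +0.63 | −29.8 | −30.0 |
| 0.70 | 0.12 | 0.0014 | 0.03 | 0.9716 | +2.60 | −29.5 | −30.0 |
| 0.60 | 0.08 | 0.0000 | 0.00 | 1.0000 | none | −39.8 | −40.0 |
| 0.60 | 0.12 | 0.0000 | 0.00 | 0.9999 | +0.56 | −39.6 | −40.0 |

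**Checks by hand.** At ratio 0.90 and log SD 0.08, the share positive is Φ(ln 0.90 / 0.08) = Φ(−1.317) = 0.094. The chance that none of 20 is positive is (1 − 0.0943)^20 = 0.138. Both agree with the table. Even with no mean change at all, the chance that all 20 values are positive is 0.5^20, about one in a million.

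**Reading.** The summary of positives only is above zero in every row where any subject is left, whatever the true change. The arithmetic mean and the back-transformed ratio both keep the right sign, and the latter returns the assumed change.

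**The case against.** The strongest reply concerns consequence. A reader might infer that the PD tables would come out empty or pointing the wrong way. The documents do not support that. The same sentence that asks for the geometric statistics also asks for n, the arithmetic mean and SD, the median and the extremes, and all of these remain valid for percentage change. Every statistic for observed sUA is sound, because concentrations are positive. The maximum-change parameters are not named in that sentence. This reply stands in full.

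Dropping non-positive values is also only one way a program might behave, and the protocol does not prescribe it. A positive geometric mean next to a negative arithmetic mean and median would be noticed by an attentive reader, and the individual values are listed. Section 11.2.1 also blanks most statistics when n is 3 or fewer, which would suppress some of these cells if n counted only the retained values. These points lower the risk. They do not make the rule executable.

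A charitable reading takes the synopsis remark on log-transformed values to mean a log ratio to baseline, back-transformed to a percentage. That would be a sensible analysis, but neither place says so, and both attach the geometric statistics to the percentage change itself. Recoding change as a positive reduction is not stated either, and it would still fail for any subject with no change or a rise. Leaving the matter to a later document is a weak answer, because Section 11.2.1 says that no separate SAP is planned and allows only an optional abbreviated one for changed analyses.

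**Conclusion.** The specification is wrong as written and should be corrected. Its reach is narrow: two of eight descriptive statistics, for one of the two sUA variables that share the list, under one secondary objective. No test, confidence interval or decision rule depends on them, and the PK comparisons and the sample size are untouched. It would be wrong to treat the point as a threat to the PD results as a whole.

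That the statistics are undefined follows from their definitions and from the protocol's own account of the drugs' direction of effect. It needs no assumed effect size. The simulated magnitudes do rest on assumed reductions of 0 to 40% and log-scale SDs of 0.08 and 0.12. A negative change is the expected direction, not a certainty for every subject and time, but a single non-positive value suffices.

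**What to change.** In Section 11.2.8 and the matching synopsis paragraph:

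- Restrict the geometric mean and geometric CV to observed sUA.
- For the raw percentage change, keep n, arithmetic mean, SD, median, minimum and maximum.
- If a log-scale summary of change is wanted, compute it on the ratio of sUA at each time to its time-matched baseline. Report the geometric mean ratio with its geometric CV, and 100 × (geometric mean ratio − 1) as the percentage change. This part is optional, since the first two changes already remove the fault.

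The cost is about two sentences of analysis text, best settled before the tables are programmed. No new data, samples or subjects are needed.
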